8.7. Recording

All sessions (CM and BSM) will be recorded. The staff member will turn on the recording device, then while recording, will inform the participant that the device has started recording and ask permission to continue. At the end of the session, the staff member will inform the participant that the device is being turned off.

Once the participant has left, the recording will be uploaded to a study computer, then uploaded to OneDrive and labeled with the Study ID, session number, group, and the staff member initials. Once the recording is uploaded, it should be deleted from the recording device and the computer (if applicable).

8.8. Tasks to Complete After the Session

8.8.1. Data Checking

Interventionists and the Research Assistant will conduct routine checks of paper forms and the questionnaires in the database following session completion. Checks regarding data fidelity (e.g., values appropriate to the field, such as age = 99) and data completeness (was a question or measure missed) will be completed. If the correct value is unknown by the Interventionist, the participant will be re-contacted to request the correct data value.

The Research Manager will be in charge of data cleaning. All data will be exported every 3 months for review and cleaning.

A data cleaning log for each session is located on OneDrive for staff to log completed data checks.

8.8.2. Gift Card Distribution

All gift cards will be pre-purchased, hard copy gift cards.

Baseline Assessment Incentive: All participants will receive a \$50 gift card for enrolling and completing a baseline visit.

Assessment Completion Incentive: After each assessment, participants will receive a \$50 gift card to their choice of store (Kroger or Walmart). Research staff will log out the gift card(s), make a photocopy of the gift card(s), and have the participant sign the photocopy to document distribution. Research staff will date the photocopy and file appropriately.

CM Group Rewards: Patients in the CM arm will have the opportunity to spin a computer number wheel if it is determined that buprenorphine is in their urine at the physician visit. If all 4 urine screens across the study duration show buprenorphine in urine, the participant will receive a \$100 bonus gift card.

This is allowed by UT policy FI0313.

8.9. Gift cards

8.9.1 Gift card ordering

The Study Coordinator will be responsible for ordering gift cards and maintaining inventory. Gift card orders should be sent to [name] via email. Orders typically take 3-6 weeks to receive.

8.9.2. Gift Card Storage

When a gift card order is received, the gift cards are stored in the Pauline 6th floor safe until they can be transported to CAS. The safe at CAS can have a maximum of \$3,000 in gift card value at any time. Gift cards and gift card log will be kept in a locked safe in a storage closet in the clinic. The safe should only be opened when a gift card is needed and only 3 staff members are allowed to have the access code to the safe per UT Fiscal Policy.

Gift cards are to be kept in the locked study safe at all times. Gift cards should only be checked out of the safe when they are ready to be disbursed to a participant. The [gift card log](#) will be kept in the safe and filled out each time a gift card is moved in or out of the safe. We will also keep a [google sheet](#) logging the incentives.

8.9.3. Gift Card Log Example

Card Number	Pin	Amount	LOG IN Initials	LOG IN Date	DISPENSE Date	LOG OUT Initials

8.9.4. Gift Card Receipt

Study ID			
Date:			

The participant and I, the research staff member, checked the balance of the gift card before distribution. We discussed that the SMART Research Study is not responsible for and will not replace lost or stolen gift cards once the gift card has been disbursed.
			
Staff Initials:		Gift Card Amount:	
Participant Initials:		Quantity:	

8.10. Option for Scheduling

Since the patient will have scheduled their next physician appointment, we will not schedule their next research appointment (unless we are remote, in which case the session will be yoked to their CAS appointment, to be scheduled immediately following their appointment at the CAS). We will use the medical charts to block off time for the participant's S1 (ex: the participant schedules a 2:00 pm doctor's appointment, their research appointment will be at 2:45 pm). Appointment times are not stringent, so if a participant gets done with their physician visit early and their assigned counselor is free, they can complete their session early.

Note on Assessment for participants who fail to attend treatment:

The study staff will continue to contact the participant to complete their assessments if a participant stops attending CAS. Study staff will inform the participant that they will not be receiving treatment (i.e., CM or BSM intervention). However, they can continue to earn gift cards for completing assessments. Assessments and intervention may occur in two visits if a participant missed their clinic visit, but later rescheduled and completed their clinic visit **before the closing of the session window.** Study staff will also inform the participant that information shared will not be disclosed to clinic staff or doctors.

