8.6. Intervention Sessions

Prior to the session, Interventionists will prepare for the brief assessment conducted during each treatment session by finding the participant in the Filemaker database, or if offline, entering the participant information on the top of the assessment materials.

Interventionists will also prepare to administer the appropriate session (1, 2, 3, or 4) (within the appropriate condition).

In addition, Interventionists will prepare the recording device to ensure that the session is recorded. If remote, the interventionist will text or email the participant a Zoom telephone number with a meeting ID for them to call and be placed in a meeting. The interventionist will ensure that Zoom is recording once permission is granted from participant. All sessions will be recorded and uploaded to OneDrive folder (SMART Project 3/Recordings) and labeled with the participant's study ID, session number (1, 2, 3, 4), condition (CM vs. BSM), and staff initials. (e.g. 301 S2 BSM AB)

At each session , the Interventionist will meet with the participant to complete the assessment questionnaires and complete the intervention – either a BSM session or a wheel spin for additional gift cards for CM (if requirements are met).

If the participant drops out of treatment at the Center for Addiction Science, they will no longer receive the CM or BSM. However, all assessments will be conducted regardless of the participant's adherence to medical treatment at the CAS. Upon completion of the assessment, participants will still earn the \$50 gift card. This will allow us to understand the reason for the participant's non-adherence to treatment, and to evaluate whether these individuals pursue treatment elsewhere.

The intervention scripts are available in section 13 of the manual of procedures.

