8.5.2. BSM Intervention Description

Record all interactions with BSM participants.

Participants who are assigned to BSM will complete their assessments with the interventionist. After the assessments are complete, the interventionist will engage the participant in the BSM intervention. A SOBER handout will be given to the participant at their baseline visit (*See section 13*). Participants will also receive a Tips for Improving Self-Control handout at session 4.

If a participant misses a session, the interventionist will continue with the next session in numerical order. So, if a participant is on S2 and missed S1, the interventionist will deliver S1 content during session 2.

This intervention consists of 4 sessions:

Session 1

This session will cover reasons for attending treatment, goals, time spent on valued activities, future events, and mindfulness-based coping (SOBER).

Session 2

This session will substance goals check in, substance free activities, and mindfulness-based coping (SOBER).

Session 3

This session will cover goals check in, substance free activities check in, and mindfulness-based coping (SOBER).

Session 4

This session will cover self-control improvement, and review goals, substance free activities, and mindfulness-based coping (SOBER).

In the event that a participant misses their clinic visit, assessments may still be completed at any time during the window. If the participant completes their clinic visit **before the session window closes** they may be contacted to complete a counseling session.

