8.6. Distressed Participant Procedures

Detecting severe emotional distress is the responsibility of all SMART staff who interact with participants.

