8.6.2. Clinic Distress Procedure

If the participant is seen in the clinic, the interventionist will follow UCH’s Behavioral Health Emergency-Suicidal Ideation procedure (policy number: BH.001), which requires that the study staff inform the behavioral specialist on staff or clinic doctor ([name]).

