12. CM INTERVENTION SCRIPT

Hi _____. Nice to see you again. As you may remember, we check on your toxicology results to determine whether you are eligible for the number wheel.

Buprenorphine Present:

I see today you do have medication in your system. Congratulations! You are eligible for the wheel spin. As a reminder, the wheel includes gift cards ranging from \$25 to \$100. You will spin and land on a random number.

<https://pickerwheel.com/>

Buprenorphine Not Present:

I see today you do not have medication in your system. I'm sorry, but you will not be eligible for the wheel spin today.

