13. BSM INTERVENTION SCRIPT

Psychosocial Intervention Session 1 (40 minutes with assessments):

Session Prep:

- a. Ensure participant has received SOBER Handout at baseline
- b. Print off blank Goals worksheet for Session 1 to fill out during session
- c. Participant should have completed the “Time Spent on Activities Worksheet” at baseline.
 - i. Have a graph of the time spent in each activity prepared and sent to the participant before the session begins
- d. Print off blank Future Event Description worksheet for Session 1 (Goals, Future Event Description) to fill out during session

1. Introduction (2 minutes)

a. Getting Permission to Record

- i. *Hi _____, is this still a good time for us to do our first session together? Great!*
- ii. *Before we get started today, I wanted to let you know all of our sessions will be recorded for the purpose of the study.*
- iii. *Do I have your permission to record this session? Thank you so much.*

b. Mandated reporting

- i. *Also, I wanted to let you know that I am a mandated reporter. That means if you let me know about any ongoing abuse, either to yourself or to someone else, or if you inform me of any intentions to harm yourself or someone else, I am obligated by law to report that. If anything like that comes up during any of our sessions, I would let you know ahead of time.*
- ii. *Do you have any questions about that?*

2. Assessment (10 minutes)

- a. Complete session one assessment forms in FileMaker.
- b. *Thank you for taking the time to answer all those questions.*
- c. *Because you finished your assessment, I will mail you that \$25 gift card. Do you prefer Kroger or Walmart? Great!*
- d. *Please allow 2-3 business days for it to arrive. If there are any issues, please don't hesitate to reach out!*

3. Build Rapport (1 minutes)

- a. *So I'd like to get to know a little more about who you are. Tell me who are the most important people in your life and one or two things you like to do – just a minute's worth of who you are.*
 - i. Wait for participant to tell you about themselves – MAXIMUM 1 minute

4. Orientation to Session (1 minute)

- a. *Thank you for telling me about yourself.*
- b. *Let me tell you about what we will be doing with our time together.*
 - i. *My overall goal is to support your treatment at the Center for Addiction Science and help you meet your goals.*

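### The non-disclosure assurance given to participants who stop attending CAS has no safety exception, so it is inaccurate for a severely distressed drop-out assessed at the clinic

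*Protocol*

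**What the plan says.** The note at the end of protocol section 8.10 covers participants who stop attending CAS. Staff keep contacting them for assessments, explain that the study intervention has ended for them, and confirm that assessments still earn gift cards. The note closes: "Study staff will also inform the participant that information shared will not be disclosed to clinic staff or doctors". No exception is attached.

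The section headed 8.6 Intervention Sessions sets the same arrangement. On the intervention: "If the participant drops out of treatment at the Center for Addiction Science, they will no longer receive the CM or BSM". On data collection: "However, all assessments will be conducted regardless of the participant's adherence to medical treatment at the CAS".

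The distress procedures are in the other section numbered 8.6, Distressed Participant Procedures. Its opening sentence concerns detection: "Detecting severe emotional distress is the responsibility of all SMART staff who interact with participants". Section 8.6.2 then deals with a participant seen in the clinic. Staff follow clinic policy BH.001, "which requires that the study staff inform the behavioral specialist on staff or clinic doctor". Section 8.6.3 deals with participants who are not at the clinic. It provides scripted questions, emergency services where there is intent or a plan, and a report of severe distress to an on-site Clinical Supervisor.

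The protocol states a limit on confidentiality in one script. BSM Session 1 includes: "if you inform me of any intentions to harm yourself or someone else, I am obligated by law to report that".

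**The concern.** The people whom section 8.10 says will not be told are the people whom section 8.6.2 says must be told. A participant who has left treatment may have reasons not to want the clinic to hear what they say, and the assurance invites them to speak freely on that basis. If such a person, sitting in the clinic, then reveals suicidal thoughts, staff must break what they have just said.

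What is at stake is the accuracy of a statement made to a vulnerable participant, and the clarity of two instructions given to the same staff. It is a participant-protection point, not an inferential one.

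**Working it through.** There is no figure to reproduce and no arithmetic applies. The check compares the instructions.

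1. **Who hears the assurance.** Participants who have stopped attending CAS and are still being assessed (section 8.10 note).

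2. **What it covers.** Information shared, without qualification. The excluded recipients are clinic staff and doctors.

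3. **Who is subject to the distress procedures.** The opening of Distressed Participant Procedures makes all study staff responsible for detecting severe distress; it does not itself require anyone to be informed. That duty comes from section 8.6.2 alone. Its condition is that the participant is seen in the clinic, and current treatment status is not part of it. Nothing in the available text exempts drop-outs.

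4. **Who must be told.** Under section 8.6.2, the behavioral specialist on staff or the clinic doctor. These recipients fall within the group excluded in step 2.

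5. **Whether the two can meet.** The documents neither require nor exclude in-person assessment of drop-outs.
   - For: section 10 treats remote delivery as the alternative when in-person work is not possible, gift cards are kept in a safe at the clinic (8.9.2), and participants sign for them (8.8.2).
   - Against: telephone access is an eligibility condition (7), the withdrawal section speaks of phone sessions (18.13.3), and the blinded follow-up is a call (3.6.3).

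6. **Whether an assessment could prompt such a disclosure.** Yes. The PHQ-2 is scheduled at every session (Table 1) and one item asks about hopelessness (12.2.25). Section 8.6.1 lists hopelessness about the future among the warning signs.

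7. **Off-site cases.** Section 8.6.3 reports severe distress to an on-site Clinical Supervisor. Whether that person counts as clinic staff or a clinic doctor is not stated, so no conflict can be shown there.

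Result: steps 1 to 4 cannot all be honoured when a drop-out is assessed at the clinic and shows severe distress. Outside that combination the text shows no contradiction.

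**The case against.** The strongest reply is that limits on confidentiality normally sit in the consent form. Section 8.2.1 says that form carries standard confidentiality and HIPAA language and that each participant receives a copy. It was not available, nor were policy BH.001 and some pages next to sections 8.6.3 and 8.10, and their absence is no fault of the plan. This limits what can be said about what participants know overall. It does not rescue the section 8.10 sentence: a limit in the consent form would leave a later, more specific oral statement at odds with it.

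A second reply is that section 8.10 summarises what staff convey and is not a verbatim script. Its evident purpose is to reassure people about answers on non-adherence or treatment elsewhere. That is a fair reading of intent. But the sentence as given to staff has no limit, whereas BSM Session 1 spells one out.

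Several stronger readings are tempting and are not supported:

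- **That staff would withhold escalation.** A reader might infer that the assurance overrides the distress procedure. Nothing in section 8.10 says so, and section 8.6.2 is a clear requirement.
- **That the assurance is false for every drop-out.** It is not shown to be so off-site (step 7). Section 8.6.3 also scripts words for distressed participants in either arm, telling them that immediate help may be needed. That is not a formal confidentiality limit and does not cover the clinic case, but it is a safeguard.
- **That the whole CM arm (20 planned, section 3.5) goes unwarned.** The CM script ("As you may remember, we check on your toxicology results to determine whether you are eligible for the number wheel") contains no mandated-reporter statement. But it also omits the permission to record that section 8.7 requires at every CM session, so it is plainly not a full list of what staff say. Its silence cannot be turned into a count, and arm size would not measure the narrow case in any event.

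In the BSM arm, the Session 1 warning survives a missed visit: "So, if a participant is on S2 and missed S1, the interventionist will deliver S1 content during session 2". By the script, someone who drops out before any BSM session would not hear it. That is context for the wording problem, not a measure of its size.

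**Conclusion.** The inconsistency is real and narrow. As written, section 8.10 has staff give an assurance that section 8.6.2 would oblige them to break for a drop-out seen in the clinic in severe distress. Three things must coincide: treatment has stopped, the assessment is in person at the clinic, and severe distress is shown. The documents give no frequency for this combination; it is probably uncommon.

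The conclusion assumes that section 8.6.2 applies to participants no longer in treatment, which its wording supports, and that nothing in the unavailable material exempts them. Severity is minor. No outcome or analysis is affected.

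**What to change.** Qualify the closing sentence of the section 8.10 note for all participants. For example: 'Information you share will not be disclosed to clinic staff or doctors, except where needed for your safety or the safety of others (section 8.6) or required by law.' Because two sections carry the number 8.6, the cross-reference should name Distressed Participant Procedures.

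This brings section 8.10 into line with section 8.6.2 and with the limit already stated in BSM Session 1. Section 8.6.2 needs no change.

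The cost is one clause and a minor IRB amendment. Candour might fall slightly. Confining the exception to safety and legal duties keeps ordinary answers, such as substance use or treatment elsewhere, under the assurance.

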8.11. Adverse Events

If patients experience an adverse event during the course of the study, we will conduct an assessment, complete an Adverse Event form, and follow the adverse event reporting system as required by our IRB and NIH regulations. We will assess Adverse Events at each intervention session.

Adverse events are defined as any untoward or unfavorable medical occurrence in a human subject, including any abnormal sign (for example, abnormal physical exam or laboratory finding), symptom, or disease, temporally associated with the subject's participation in the research, whether or not considered related to the subject's participation in the research.

Serious adverse events are any adverse event temporally associated with the subject's participation in research that meets any of the following criteria:

- (1) results in death;
- (2) is life-threatening (places the subject at immediate risk of death from the event as it occurred);
- (3) requires inpatient hospitalization or prolongation of existing hospitalization;
- (4) results in a persistent or significant disability/incapacity;
- (5) results in a congenital anomaly/birth defect; or
- (6) any other adverse event that, based upon appropriate medical judgment, may jeopardize the subject's health and may require medical or surgical intervention to prevent one of the other outcomes listed in this definition

At every session, we will assess both Adverse Events and Serious Adverse Events (AEs and SAEs).

All SAEs related to study participation are to be reported to the Project Manager who will report to the Study Physician (e.g., [name] [name]) within 24 hours of occurrence, and are to be reported to the UTHSC IRB immediately.

UTHSC's IRB operating procedures regarding AE's can be found here:

<https://www.uthsc.edu/research/compliance/irb/researchers/documents/adverse-event-reporting.pdf>

We do not anticipate any study related SAEs (we haven't observed treatment related SAEs in any of our studies) as our study involves an over-the-counter medication and psychosocial intervention.

A copy of the Adverse Events reporting tool is located in the Measures section.

8.12. Participant Retention for Enrolled Participants

If a participant is having difficulty participating in sessions regularly, it is the job of the Interventionist to find out obstacles to treatment and work with the participant to overcome these obstacles.

Once a participant is enrolled, it is the Interventionist's goal is to retain them in the study.

In addition to FileMaker, Interventionists should regularly update the Retention Log in OneDrive with their active participants. Interventionists have the flexibility to provide participants whatever form of treatment is needed to retain them in the study. Before offering participants special arrangements, Interventionists will review these cases with the Study Team.

Procedures are in place to assist you in retaining participants. These include incentives for assessments (\$50 gift cards), as well a t-shirt and welcome bag (snacks and cloth face mask) that will be provided at enrollment.

8.12.1. Standard Interventionist Retention Skills

Always take a positive approach with the patient. Always be understanding of their situation.

Acknowledge situation when appropriate, (e.g., condolences for a recent family death; inquiring how they are doing when ill or hospitalized.)

Always document the reason a participant did not participate and any suggested approach for handling the missed session. Also document on the Process Note any participant circumstances that we may want to stay aware of (e.g., death in family, illness).

Standard retention practices include:

- Birthday cards
- Holiday cards
- Reminders pre-session (day before)

